16.1.4 General Specifications for PK Concentration and PK Parameter Data

Predose samples that occur before the first drug administration will be assigned a time of 0 hours, as if the sample had been taken simultaneously with the study intervention administration.

Predose or trough samples which have been taken after the subsequent dosing will be reported as a protocol deviation. The resulting concentrations will be included in concentration listings but excluded from descriptive statistics of concentrations and from PK parameter estimation.

Values BLQ will be taken as zero for summary statistics of PK concentration data, PK parameter estimation (e.g., AUC) and for graphical presentations.

Missing concentrations (e.g., no sample, insufficient sample volume for analysis, no result or result not valid) will be reported generally as "N.R.". A participant who withdraws prior to the last planned observation will be included in the analyses up to the time of discontinuation if still included in the PK analysis set.

If samples are collected outside of the PK sampling time windows defined in the CSP in Section 8.4, these will be included in the PK parameter estimation (NCA) but will be excluded from the concentration summary and mean/median concentration plots.

PK concentrations which are erroneous due to a sampling processing or analytical error (as documented in the bioanalytical report) may be excluded from the PK analysis if agreed by the Sponsor. In this case the rationale for exclusion will be provided in the CSR. Any other PK concentrations that appear implausible to the Clinical Pharmacologist/Clinical PK/PD Scientist will not be excluded from the analysis. Any implausible data will be documented in the CSR.

If important protocol deviations occurred likely to affect the PK profile of participants as specified in Section 10.2.1, the impacted concentrations and PK parameters will be excluded from summary statistics and further statistical evaluation.

Any PK concentrations or PK parameters excluded from summary statistics will be included in participants listings and flagged; a reason for exclusion will be detailed in the CSR (e.g., a footnote or a table of exclusions). Any flags will be included in the study specific CDISC data sets.

PK concentrations and PK parameters excluded from summary statistics will not be included in mean/median figures. Mean plots will only contain values where $n > 2$.

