10.2 Protocol Deviations / Exclusion from Analysis Sets

10.2.1 Important Protocol Deviations

Listings of important protocol deviations will be provided including the date and relative day in relation to dosing in the relevant period. A distinction will be made between important protocol deviations due to COVID-19 versus not due to COVID-19. The respective important protocol deviations will be flagged accordingly.

Important protocol deviations or important events that might influence PK include, but may not be limited to the following:

- Adverse events, diarrhea etc. (these instances will be discussed on a case-by case basis)
- Vomiting after administration following oral dosing (these instances will be discussed in alignment with applicable regulatory guidelines on a case-by-case basis)
- Sample processing errors that may lead to inaccurate bioanalytical results
- Inaccurate dosing or dosing errors (e.g., dose administration delayed, dose change or missed doses)
- Predose or trough sample collected after the actual dosing
- Non-compliance with food and drink requirements (e.g., non-fasted, incomplete meal consumption, caffeine intake)
- Concomitant medication, vitamins, dietary or herbal supplements

Should one or more of these events be available at the Data Review Meeting, its implication for PK evaluation will be discussed and agreed amongst relevant study team members (e.g., Sponsor Clinical Pharmacology/Biostatistics/Clinical Pharmacokinetics & Pharmacodynamics team representative). Appropriate action will be taken such as flagging individual values to be excluded from analysis.

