16.1.5.1 Estimation of Pharmacokinetic Parameters in Plasma

PK parameters will be calculated using the actual elapsed time since dosing. If the actual sampling time is missing, calculations may be performed using the scheduled time. Details (e.g., number of samples, participants affected) will be described in the CSR. If actual dosing time is missing, scheduled time might be used for NCA after performance of adequate plausibility checks and agreement with the sponsor. Decision and rational should be included in the CSR. Otherwise, there will be no further imputation of missing data.

The following plasma PK parameters will be calculated, when appropriate, for evobrutinib on Day 1 for each period:

Symbol	Definition
$AUC_{0-\infty}$	The AUC from time zero (= dosing time) up to infinity with extrapolation of the terminal phase.
$AUC_{0-t_{last}}$	The AUC from time zero (= dosing time) to the time of the last quantifiable concentration (t_{last}).
C_{max}	Maximum observed concentration.
t_{max}	The time to reach the C_{max} in a dosing interval.
$t_{1/2}$	The terminal half-life.
t_{lag}	The time prior to the first concentration at or above LOQ.
CL/F	The apparent total body clearance following extravascular administration.
V_z/F	The apparent volume of distribution during the terminal phase following extravascular administration.
F_{rel}	Relative Bioavailability [%] of each Batch in relation to the Reference Batch (treatment A) will be calculated: $F_{rel} = 100 \times (AUC_{0-\infty} \text{ [Batch]} \times \text{Dose}_{\text{[Reference Batch]}}) / (AUC_{0-\infty} \text{ [Reference Batch]} \times \text{Dose}_{\text{[Batch]}})$
λ_z	Terminal first order (elimination) rate constant.

Additional PK parameters may be calculated where appropriate.

Units for PK parameter outputs will be based on concentration and dose units used in the study, unless otherwise specified. If concentration data units change within the study, PK parameters will be reported using consistent units throughout study outputs. In such cases, the Sponsor will specify relevant units for reporting before the final PK evaluation.

The parameters C_{max} and t_{max} will be obtained directly from the concentration-time profiles. If C_{max} occurs at more than one timepoint, t_{max} will be assigned to the first occurrence of C_{max} .

The following PK parameters will be calculated for diagnostic purposes and listed, but will not be summarized:

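### Does the SAP give two conflicting rules for excluding a concentration affected by a sample-processing error?

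*SAP*

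**What the plan says.** SAP 16.1.4 has two adjacent paragraphs on exclusions.

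- The first concerns single erroneous values. Concentrations in error because of "a sampling processing or analytical error (as documented in the bioanalytical report) may be excluded from the PK analysis if agreed by the Sponsor". The reason must then be given in the study report. The same paragraph rules out removing a value merely because it looks implausible.
- The second concerns important protocol deviations likely to affect a participant's PK profile. For those, "as specified in Section 10.2.1, the impacted concentrations and PK parameters will be excluded from summary statistics and further statistical evaluation".

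SAP 10.2.1 is the list to which the second paragraph refers. It includes "Sample processing errors that may lead to inaccurate bioanalytical results". It then sends every listed event to the Data Review Meeting, where the team agrees what it means for the PK evaluation. After that: "Appropriate action will be taken such as flagging individual values to be excluded from analysis". SAP 6 places this meeting before database lock.

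Three other provisions bear on the point.

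- SAP 16.1.4 counts a result that is not valid among the missing concentrations, reported as N.R.
- SAP 16.1.5.1 says that Cmax and tmax "will be obtained directly from the concentration-time profiles", and adds: "Otherwise, there will be no further imputation of missing data".
- Under SAP 16.1.4, values left out of the summaries "will be included in participants listings and flagged", with the reason in the study report.

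**The concern.** A processing error that corrupts one plasma sample can be read under either paragraph of SAP 16.1.4. The two differ in three ways:

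- force: exclusion is optional in one and required in the other;
- condition: sponsor agreement in one, none stated in the other;
- level: the concentration only, or also the PK parameters that depend on it.

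No sentence gives one paragraph precedence.

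This would matter most if the sample were at the peak. Cmax is a primary endpoint taken straight from the observed profile, so the same error could lead to three data sets: the bad value kept, the next-highest sample used as Cmax, or that participant-period removed from the Cmax model. If the affected profile belonged to batch A, the reference, all three batch ratios would move together. The study is open-label and the sponsor takes part in the decision, so a choice between rules made after concentrations are known would be discretion over the primary result.

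**Working it through.** **Reading the text.** Set side by side, the provisions narrow the conflict.

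| Step | Provision | Consequence |
|---|---|---|
| Result declared not valid | SAP 16.1.4, missing concentrations | Already missing; neither exclusion rule is needed |
| Result reported but documented as erroneous | SAP 16.1.4, first paragraph | Concentration may be removed with sponsor agreement |
| Event on the 10.2.1 list | SAP 10.2.1 | Implication for PK agreed at the Data Review Meeting, then action |
| Deviation likely to affect the profile | SAP 16.1.4, second paragraph | Whatever is *impacted* is removed |

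The second paragraph removes only impacted values. If the bad concentration is taken out before the noncompartmental analysis and lies away from the peak, Cmax is not impacted, and both paragraphs lead to the same Cmax. They part only when the lost sample is at or next to the observed peak.

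**Size when they part.** The documents state no figure to reproduce. Inputs:

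- n = 28: 4 sequences with at most 7 participants each (protocol 6.3.1);
- the four printed Williams sequences, and a log-scale model with batch, period and participant (SAP 16.1.3; participants taken as fixed, which gives the same batch contrasts in complete data);
- assumed: within-participant CV 30% (range 20–40%), an error that doubles the peak reading (range 1.5–3 times), and a one-compartment oral profile with tmax 0.5–1.5 h and half-life 1.5–6 h at the protocol sampling times.

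In this balanced design, one batch-B log value has weight 1/28 on B/A and 0 on C/A and D/A. One batch-A value has weight -1/28 on all three ratios. A relative error f in one batch-B Cmax therefore shifts B/A by f^(1/28) - 1.

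1. *Bad value kept.* 2^(1/28) - 1 = +2.5%; at 1.5 times +1.5%, at 3 times +4.0%. In a batch-A profile, 2^(-1/28) - 1 = -2.4% on every ratio.
2. *Concentration dropped.* The next-highest sample becomes Cmax. In the assumed profiles it is between 0.87 of the peak sample and almost equal to it. The shift runs from 0.87^(1/28) - 1 = -0.5% to 0.0%.
3. *Parameter dropped.* The expected shift is 0. The model has 28 + 3 + 3 = 34 parameters for 112 observations, so each observation has leverage 34/112 = 0.304. The SD of the change in the log ratio from deleting one value is s/(28 × √(1 - 0.304)), with s = √ln(1 + CV²). At CV 30%, s = 0.294 and the SD is 0.0126. The mean absolute change is 0.0126 × √(2/π) = 0.010, or 1.0% (0.7% at CV 20%, 1.3% at CV 40%).
4. *Yardstick.* The 90% CI half-width is exp(t × s × √(2/28)) - 1, with 3 × 28 - 6 = 78 degrees of freedom and t = 1.665. At CV 30% it is exp(1.665 × 0.294 × 0.267) - 1 = 14% (9% at CV 20%, 19% at CV 40%).

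The comparison between the two rules, given exclusion, is line 2 against line 3: a bias of at most half a percent against a zero-mean change of about 1%. Line 1 arises only if a documented error is deliberately retained.

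**The case for a change.** The strongest case for a change is that the SAP settles neighbouring situations firmly. Predose samples taken after dosing, out-of-window samples and implausible values each have a fixed treatment. The case-by-case wording in 10.2.1 is attached to adverse events and to vomiting ("discussed in alignment with applicable regulatory guidelines on a case-by-case basis"), not to processing errors. Two readings might separate the paragraphs: bioanalytical report versus deviation log, or a faulty measurement versus a disturbed profile. The SAP draws neither line explicitly, and one error could appear in both records. Nor does it say that the decision is taken without knowledge of batch. A clarifying sentence would cost almost nothing.

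The textual part of this stands: the overlap exists, and a tidier document would remove it. The inference to a needed change does not. The agreement step in 10.2.1 covers every item on its list, processing errors included, so it qualifies the mandatory wording that refers back to that list. The room for outcome-driven choices is also limited: the permissive rule requires the error to be documented in the bioanalytical report, and a value cannot be dropped for looking wrong. Merely asking for one rule would not say which is better. Removing only the concentration keeps the participant-period but can understate Cmax slightly; removing the parameter avoids that and loses a data point. Which suits a given case depends on where the sample lies on the curve, and a team looking at the profile can judge that.

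**Conclusion.** The two paragraphs of SAP 16.1.4 do overlap for sample-processing errors, but the gap is one that analysts fill sensibly. The route is already there: treat an invalid result as missing, agree the consequence of a documented error before database lock, remove what is impacted, and list, flag and explain it. A reader of the study report could recompute the effect of any exclusion.

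The choice between rules is worth about 1% or less on average in one Cmax ratio for one affected batch-B peak sample, against a 90% CI half-width near 14%. The larger shift of about 2.5% requires a twofold documented error at the peak to be kept. These sizes rest on the assumed CV, error size and profile shape, and on the maximum of 28 participants. Protocol 9.1 describes the analysis as purely descriptive, with no hypothesis tests. No change to the plan follows.

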16.1.5 Estimation of Pharmacokinetic Parameters

The computer program Phoenix® WinNonlin® version 7.0, or higher (Certara, L.P., Overlook Center, Suite101, Princeton, NJ 08540) will be used to derive PK parameters applying NCA.

The statistical software SAS® (Statistical Analysis System, SAS-Institute, Cary NC, USA, windows version 9.4 or higher) will be used to generate additional PK parameters and produce tables, listings, and figures.

16.1.5.1 Estimation of Pharmacokinetic Parameters in Plasma

PK parameters will be calculated using the actual elapsed time since dosing. If the actual sampling time is missing, calculations may be performed using the scheduled time. Details (e.g., number of samples, participants affected) will be described in the CSR. If actual dosing time is missing, scheduled time might be used for NCA after performance of adequate plausibility checks and agreement with the sponsor. Decision and rational should be included in the CSR. Otherwise, there will be no further imputation of missing data.

The following plasma PK parameters will be calculated, when appropriate, for evobrutinib on Day 1 for each period:

Symbol	Definition
$AUC_{0-\infty}$	The AUC from time zero (= dosing time) up to infinity with extrapolation of the terminal phase.
$AUC_{0-t_{last}}$	The AUC from time zero (= dosing time) to the time of the last quantifiable concentration (t_{last}).
C_{max}	Maximum observed concentration.
t_{max}	The time to reach the C_{max} in a dosing interval.
$t_{1/2}$	The terminal half-life.
t_{lag}	The time prior to the first concentration at or above LOQ.
CL/F	The apparent total body clearance following extravascular administration.
V_z/F	The apparent volume of distribution during the terminal phase following extravascular administration.
F_{rel}	Relative Bioavailability [%] of each Batch in relation to the Reference Batch (treatment A) will be calculated: $F_{rel} = 100 \times (AUC_{0-\infty} \text{ [Batch]} \times \text{Dose}_{\text{[Reference Batch]}}) / (AUC_{0-\infty} \text{ [Reference Batch]} \times \text{Dose}_{\text{[Batch]}})$
λ_z	Terminal first order (elimination) rate constant.

Additional PK parameters may be calculated where appropriate.

Units for PK parameter outputs will be based on concentration and dose units used in the study, unless otherwise specified. If concentration data units change within the study, PK parameters will be reported using consistent units throughout study outputs. In such cases, the Sponsor will specify relevant units for reporting before the final PK evaluation.

The parameters C_{max} and t_{max} will be obtained directly from the concentration-time profiles. If C_{max} occurs at more than one timepoint, t_{max} will be assigned to the first occurrence of C_{max} .

The following PK parameters will be calculated for diagnostic purposes and listed, but will not be summarized:

- First (λ_z low) and last (λ_z up) time point of the time interval of the log-linear regression to determine λ_z .
- Number of data points (N_z) included in the log-linear regression analysis to determine λ_z .
- Goodness of fit statistic (adjusted R^2) for calculation of λ_z .
- AUC from time t_{last} extrapolated to infinity given as percentage of $AUC_{0-\infty}$ ($AUC_{extra\%}$).
- Span ratio of interval over which $t_{1/2}$ was estimated/ $t_{1/2}$.

The regression analysis should contain data from at least 3 different time points in the terminal phase consistent with the assessment of a straight line on the log-transformed scale. Phoenix WinNonlin “best fit” methodology will be used as standard. If warranted, further adjustment may be made by the pharmacokineticist, after agreement with the Sponsor. The last quantifiable concentration $> LLOQ$ should always be included in the regression analysis, while the concentration at t_{max} and any concentrations BLQ which occur after the last quantifiable data point $> LLOQ$ should not be used.

If $AUC_{extra\%} > 20\%$ and/or the coefficient of correlation (R^2 adj) of λ_z is < 0.8 and/or the observation period over which the regression line is estimated (span ratio) is less than 2-fold the resulting $t_{1/2}$, the rate constants and all derived parameters (e.g. $t_{1/2}$, $AUC_{0-\infty}$, CL/F , etc.) will be

listed, flagged and included in the parameter outputs. Should more than 10% of subjects be flagged for AUC_{extra} and/or Rsq adj (for a particular analyte), a sensitivity analysis excluding flagged parameters may be performed after discussion with the Sponsor.

16.1.6 Presentation of PK Concentration and PK Parameter Data

16.1.6.1 Listings and Tables

The following PK tables will be produced (PK Analysis Set):

- Descriptive statistics of plasma concentrations by nominal time and study intervention
- Descriptive statistics of plasma PK parameters by study intervention

The following PK Listings will be produced (Safety Analysis Set):

- Individual plasma concentrations by nominal time, participant, and study intervention sorted in chronological order
- Individual plasma PK parameters by participant and study intervention
- PK sampling date, actual time, nominal time, deviation from time, percentage time deviation by participant, and study intervention sorted in chronological order
- Phoenix® WinNonlin® NCA Core Output

16.1.6.2 Graphical Summaries and Individual plots (PK Analysis Set)

The following graphical summaries and individual plots will be provided:

- Overlaid individual plasma concentration versus time plots on linear and semi-log scale, using actual times, by study intervention
- Overlaid individual plasma concentration versus time plots by participant on linear and semi-log scale using actual times. If any postdose concentration is BLQ the line representing LLOQ will be added to the semi-log plots
- Arithmetic mean concentration time plots; linear ($\pm SD$ for arithmetic mean) and semi-log; using scheduled (nominal) time points by study intervention; if any postdose concentration is BLQ the line representing LLOQ will be added to the semi-log plots
- Median concentration time plots; linear and semi-log; using scheduled (nominal) time points by study intervention; if any postdose concentration is BLQ the line representing LLOQ will be added to the semi-log plots
- Boxplots for primary PK parameters $AUC_{0-\infty}$ and C_{max} by study intervention
- Spaghetti plot of primary PK parameters by study intervention

17 References

Not applicable.

18 Appendices

Not applicable.
